As teduglutide was approved by the FDA for short gut syndrome in December 2012, it is still fairly new to market, so there may be yet some unknown side effects outside of those reported in the clinical trials, but data is being collected in an FDA-required postmarketing study of patients with short bowel syndrome treated with teduglutide in the clinical setting to further evaluate the drug's long-term safety. In our proposed randomized study, we will monitor patients at each visit for possible symptomatic side effects. In addition, we will also follow the necessary recommended safety testing at baseline and at safety interim visits in the study. Patients with known malignancy within the last 5 years, history of colon cancer, or first degree relative with colon cancer will be excluded from the study. Screening colonoscopy will identify participants with previously undiagnosed colon cancer, whom we will exclude from the interventional study. All interventional study participants will undergo a colonoscopy at the end of the study. Women who are pregnant, planning on becoming pregnant, or are breastfeeding will be excluded from the study.

Radiation Risks:

The estimated median dose of CCTA is 4 mSv. Individual dose will vary, as each exam is tailored to the subject's size, heart rate, and rhythm. This tailored approach along with the state-of-the-art dose reduction techniques described above allow the dose to be substantially lower than historically reported median CCTA doses (please see references from MGH below).

References for CCTA dose at MGH:

Ghoshhajra, B. B., Engel, L.-C., Major, G. P., Goehler, A., Techasith, T., Verdini, D., et al. (2012). Evolution of coronary computed tomography radiation dose reduction at a tertiary referral center. The American journal of medicine, 125(8), 764–772. doi:10.1016/j.amjmed.2011.10.036

Engel, L.-C., Lee, A. M., Seifarth, H., Sidhu, M. S., Brady, T. J., Hoffmann, U., & Ghoshhajra, B. B. (2013). Weekly dose reports: the effects of a continuous quality improvement initiative on coronary computed tomography angiography radiation doses at a tertiary medical center. Academic Radiology, 20(8), 1015–1023. doi:10.1016/j.acra.2013.04.012

Ghoshhajra, B. B., Engel, L.-C., Károlyi, M., Sidhu, M. S., Wai, B., Barreto, M., et al. (2012). Cardiac Computed Tomography Angiography With Automatic Tube Potential Selection: Effects on Radiation Dose and Image Quality. Journal of thoracic imaging, 1–9. doi:10.1097/RTI.0b013e3182631e8a

Radiation exposure for a low dose CT scan of the abdomen is about 0.10 mSV per slice.

For FDG-PET/CT, the administered dose from F-18 FDG for a typical cardiac study is 370 MBq (10 mCi) and the effective dose for an attenuation correction scan of head/neck/chest/upper abdomen is about 2.8 mSv. The total effective dose from two FDG-PET/CT studies would be 20 mSv.

The total radiation dose associated with this study is approximately 28 mSv and is about the same as one would normally receive in approximately 9 years from background radiation.

Blood drawing:

The maximum total blood drawn for a patient completing the 6 month long interventional study is approximately 502 ml for participants with HIV and 226 ml for participants without HIV. There will be minimal risk and discomfort associated with blood drawing and IV placement. The risks of these procedures are minor bruising or bleeding at the site of the blood draw or IV catheter, nausea from the glucose infusion, and lightheadedness from the blood draws.

The maximum total blood drawn for a patient completing only the cross-sectional substudy is approximately 150 mL.

For each participant, blood will not be drawn more than twice per week and the total amount will not exceed 550mL in an 8-week period. Blood sampling exceeding 200mL will not be drawn at any one point in time.

Genetic Research Studies:

Genetic research studies may create special risks to human subjects and their relatives. These involve medical, psychosocial and economic risks, such as the possible loss of privacy, insurability and employability, change in immigration status and limits on education options, and may create a social stigma. Knowledge of one's genetic make-up may also affect one's knowledge of the disease risk status of family members. To minimize the risks associated with genetic testing, no results will be filed in the subject's medical record and no research results will be given to subjects or healthcare providers.

CT contrast medium:

This procedure requires the injection of an iodinated contrast medium. These contrast media have been known to cause renal failure, particularly in patients with a pre-existing renal impairment. The contrast dose in cardiac CT has decreased with the introduction of faster scanners. The dose required in 128-slice CT will be between 60 and 120 ml. Anaphylactoid (allergic-type) reactions to iodinated contrast media may case skin reactions or in very rare occasions result in breathing difficulty and hypotension (shock). Patients with previous reactions to iodine-containing contrast media will be excluded from participation.

Participants with signs of renal failure will not be included in the study. Typical contrast dose during a cardiac CT exam translates into $\sim 1 \text{ ml/kg}$ in an average patient.

In participants with normal renal function the elimination half-life of iodine-containing contrast media is 2 hours and 99% is excreted after 24 hours. This is irrespective of the total amount of contrast. Unless the patient has elevated creatinine levels, we can safely assume that all contrast is eliminated after one day.

The following additional safety criteria will be implemented. Participants will be excluded if:

- · Serum creatinine > 1.5 mg/ml
- The estimated creatinine clearance < 60 ml/min

Rarely, complication of IV contrast extravasation may occur.

Beta-blockers:

Beta-blockers are used by millions of Americans and are generally considered safe. The side-effects and risks of incidental (incremental) use of beta-blockers include bradycardia (which is the purpose of the administration), hypotension, and in rare occasions wheezing (bronchospasm) and dyspnea. Allergic reactions to beta-blockers are rare.

Nitroglycerin:

Nitroglycerin is routinely used in clinical CT coronary angiography and the treatment of angina pectoris, and is generally considered safe. The side-effects and risks of nitroglycerin are generally mild and of short duration and include hypotension, tachyarrhythmia, headache, lightheadedness, and visual disturbance. Subjects who are on sildenafil, tadalafil, or vardenafil will need to stop these drugs at least 5 days prior to receiving nitroglycerin on the day of the cardiac CT scan. Nitroglycerin will not be administered to subjects who have taken sildenafil, tadalafil, or vardenafil within 5 days of the cardiac CT scan. If baseline systolic blood pressure is below 90, nitroglycerin will not be given. If a participant's blood pressure were to drop precipitously or if the participant develops symptoms, standard clinical resuscitative care will be given. For hypotension, intravenous boluses of normal saline will be administered and the subject will be closely monitored. If there is no response to intravenous volume resuscitation, then pressor agents will be administered as per standard clinical practice.

Pregnancy and urine tests:

Urine pregnancy test will be performed in female participants at each visit. Female participants will be cautioned carefully about the risks of the study and pregnancy. If a female participant were to become pregnant at any time point during the study, the study drug will be immediately stopped and no radiologic procedures will be performed.

Questionaires and Neurocognitive Testing:

Subjects will be instructed to complete the questionnaires to the best of their ability, but will have the option to leave any question(s) blank. In the unlikely event that evidence of a new physical or psychological disorder is found, with the individual's permission, the information will be shared with his or her primary care physician who can direct care as needed. There are minimal risks associated with completing questionnaires and neurocognitive testing and include subject fatigue and the possibility of minor psychological distress associated with answering sensitive questions regarding psychological functioning. As detailed, the investigators will be careful regarding the protection of confidentiality, and multiple procedures are in place to reduce the likelihood of a breach of confidentiality.

VIII. Potential Benefits

There may be no direct benefit to the individual participant. As part of the study, participants may undergo: 1) the examination of the colon which might reveal polyps, cancers, vessel abnormalities, lymphomas, or other disorders that need treatment; and 2) determination of coronary calcium score, coronary anatomy and pathology. Participants and their healthcare provider (with the participants' permission) will be informed of any abnormal findings of clinical relevance in a timely fashion. In the event that neurocognitive impairment or high depressive symptoms are found, with the participant's permission, the information will be shared with his or her primary care physician who can direct care as needed, and will include information to neurology or psychiatry-infectious disease specialists for appropriate medical care and counseling. Patients who are initially screened for the HIV uninfected control group who are found to have a positive HIV ELISA test at study entry, will be immediately contacted and will be referred to an infectious disease specialist for appropriate medical care and counseling.

Potential benefits to society include an increased understanding of the mechanisms of atherosclerotic disease in the HIV-infected population and immune or intestinal factors that may be associated with atherosclerosis in this patient population. Additional potential benefits to society include an increased understanding of the mechanisms of neurocognitive impairment and depression in the HIV-infected population and immune or intestinal factors that may be associated with these conditions.

IX. Monitoring and Quality Assurance

The principal investigator (PI) will continually monitor the study. She will ensure that adverse events are reviewed promptly and reported to the Partners Human Research Committee (PHRC) as per PHRC policy. A data and safety report will be included in the annual report to the PHRC. Any serious adverse events will be reported within 24 hours to the PHRC.

The data and safety monitoring board (consisting of a gastroenterologist, a HIV specialist, and a cardiologist) will meet regularly every 6 months to review all adverse events and will be called upon at other times also as significant adverse events arise.

The PI and study team will review all adverse events on a case-by-case basis. The PI and study team will also be reviewing all adverse events with the DSMB every 6 months and all serious adverse events when they arise.

Unanticipated problems including adverse events will be reported to the Partners Human Research Committee (PHRC) as described in the PHRC policy on Unanticipated Problems Involving Risks to Subjects or Others including adverse events:

http://healthcare.partners.org/phsirb/Guidance/Reporting_Unanticipated_Problems_including_Adverse_E_vents.1.11.pdf

The PI, [name], will report to the PHRC any of the following unanticipated problems and adverse events that occur: 1) during the conduct of the study, 2) after study completion, or 3) after subject withdrawal or completion. Reports are to be submitted within 5 working days/7 calendar days of the date the investigator first becomes aware of the problem.

- Internal adverse events that are unexpected, and related or possibly related to the research and that indicate there are new or increased risks to subjects;

- External adverse events that are serious, unexpected, and related or possibly related to the research and that indicate there are new or increased risks to subjects that require some action (e.g., modification of the protocol, consent process, or informing subjects);

- Unanticipated adverse device effects that are serious and caused by, or associated with, the device;

- Deviation from the approved research protocol or plan without IRB approval in order to eliminate apparent immediate hazard to subjects or harm to others;

- Deviation from the approved research protocol or plan that placed subjects or others at an increased risk of harm regardless of whether there was actual harm to subjects or others;

- Any event that requires prompt reporting according to the research protocol or investigational plan or the sponsor;

- Breach of confidentiality or violation of HIPAA (e.g., lost or stolen laptop);

- Medication, procedural or laboratory error (e.g., errors in drug administration or dosing, surgical or other procedure, or testing of samples or test results) regardless of whether subjects experienced any harm;

- Interim analysis, safety monitoring report, publication in a peer-reviewed journal, or other finding that indicates that there are new or increased risks to subject or others or that subjects are less likely to receive any direct benefits from the research;

- Change in FDA labeling (e.g., black box warning), withdrawal from market, manufacturer alert from the sponsor, or recall of an FDA-approved drug, device, or biologic used in the research;

Reporting of unanticipated problems that are adverse events: Any unanticipated untoward or unfavorable medical occurrence, including abnormal sign (for example, abnormal physical exam or laboratory finding), symptom, or disease, that indicates that the research places subjects at increased risk of physical or psychological harm than previously known or recognized will be reported to the Partners IRB within 5 working days/7 calendar days of the date the principal investigator first becomes aware of the problem according to Partners Human Research Committee (PHRC) Policy.

Subjects will be informed about any incidental findings found on any of the study procedures obtained in the study. If the subject grants permission, the study investigator will also inform the subject's primary care physician (PCP). If the finding requires that the subject be referred to a specialist, we will make a recommendation to the subject and the PCP and offer to facilitate the referral, but will defer to the PCP to make the final decision.

In an effort to maximize the safety of subjects, those subjects who are taking anticoagulants, that require antibiotic prophylaxis for invasive procedures, and who have an allergy/intolerance/sensitivity to benzodiazepines have been excluded from participation.

Colonoscopies will be performed in the GI Endoscopy Unit at MGH by the gastroenterologist coinvestigator. A member of the study staff will be present at the procedures.

Subjects will be discontinued from the study if they develop elevated creatinine >2 mg/dl, rise in AST or ALT > 5x upper limit of normal, pancreatitis, malignancy or become pregnant. Subjects will be instructed to immediately report significant symptoms including, but are not limited to abdominal pain, nausea, injection site reactions, and swelling. These symptoms will be carefully monitored and subjects with intolerable side effects may be discontinued. In additional, subjects who develop generalized hypersensitivity will also be discontinued from the study.

The investigators and study staff will take measures to protect the privacy of patients. Study-specific Data Collection/Case Report Forms will be completed for all subjects who consent to study participation. In order to further protect the privacy and confidentiality of subjects, subject data and case report forms will be labeled with an alphanumeric code and will not contain the subject's name, initials, medical record number, date of birth or social security number. The key to the code which links subject's identity to the code will be kept in a secure location separate from the case report forms, subject data and documents. Subject clinical source documents include: laboratory reports, procedure reports, and radiologic reports. All study records will be maintained in a secure fashion with access limited to essential study personnel only.

The PI will review the case report forms and source documents quarterly and periodically as the need arises. An internal audit will be conducted annually for both subject and regulatory study files. Accuracy of data entered into the database will be verified with source documents. The PI and study team will discuss and review research results and corresponding data on a regular basis at laboratory meetings.

X. References

1. Lohse N, Hansen A-BE, Pedersen G, et al. Survival of Persons with and without HIV Infection in Denmark, 1995-2005. Ann Intern Med 2007;146:87-95.

2. Palella FJ, Jr., Baker RK, Moorman AC, et al. Mortality in the highly active antiretroviral therapy era: changing causes of death and disease in the HIV outpatient study. J Acquir Immune Defic Syndr 2006;43:27-34.

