Overview of the Approach: A total of 90 subjects (70 subjects with chronic HIV-1 infection and 20 HIVnegative control subjects) will be recruited (See Figure 2). For the neurological substudy, an additional 15 HIV-negative control subjects will be recruited and complete Visit A and Visit B (see Figure 1b, not shown in Figure 2 flowchart). Ninety subjects will complete **Baseline Study Part 1** of the cross-sectional study. **Baseline Study Part 2** will be performed in a subset of 60 HIV-infected patients and 10 HIVnegative controls. The 60 HIV-positive patients who complete Baseline Studies Part 1 and Part 2 will enter the **Randomized Study of Teduglutide vs. Placebo**. The tests and procedures obtained during the Baseline Studies Part 1 and Part 2 for these 60 HIV-positive participants will serve as the baseline measurements for the randomized study (they are not repeated) in order to minimize risk from exposure to study procedures for the participants and to maximally utilize the study data.

Having the control group will help us establish whether assessed relationships between GI epithelial integrity, microbial translocation, immune activation, and cardiovascular imaging markers are HIV-specific. Adding the neurological substudy control group (n=15) will help us potentially identify a HIV-

specific, cardiovascular and inflammatory link to cognitive impairment and depression. The control group can also serve as a comparison group with which to compare the HIV patients.

Figure 2

After all subjects have completed the study, transcriptomic profiling by RNA-Seq will be performed in 7 HIV+ participants with greatest degree of coronary disease seen on CTA vs. 7 HIV+ participants without and 7 HIV+ participants with the greatest degree of bacterial translocation vs. 7 HIV+ participants with the least amount of microbial translocation.

Participants will be recruited from the Boston area from infectious disease clinics, HIV community centers and also via IRB-approved advertisements. Patients will also be recruited via referral by primary care providers, infectious disease providers, newspaper advertisement, posted flyers, and Partners subject recruitment broadcast. After obtaining informed consent, baseline measurements and studies will be performed.

Inclusion criteria for HIV-infected participants:

- 1. Men and women age 21-65 with previously diagnosed HIV disease

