*Multivariate modeling:* For outcomes TBR and plaque, to control for potential confounders, multivariate linear regression modeling will be used to identify factors independently associated with increasing TBR and increasing number of atherosclerotic plaque lesions. Similar methods will be applied for neurocognitive score and mood assessment to cerebral FDG-PET/CT. Model variable selection will be based on "change-in-estimate" method⁵⁸. Candidate covariates to be chosen for entry into our model include all covariates significant on individual univariate models (p<0.05), potential confounders, and biologically plausible covariates with established relationships to atherosclerosis. Colinearity among covariates will be identified and redundant covariates will be excluded from the model. Confounders will be identified by observing changes in effect estimate β ; colinearity will be identified by observing changes in effect estimate β ; as well as by using Variance Inflation Factor criterion. Regression diagnostics will be used to check if model assumptions are met⁵⁸. We will control for age, gender, race, smoking, lipids, diabetes mellitus, WRAT 4 reading versus educational years, and hypertension in addition to other potential confounders identified by methods above.

Between group comparisons: We will also assess differences in microbial translocation, mucosal immunity and GI permeability markers among those with coronary atherosclerosis vs. those without atherosclerosis and in those with elevated TBR (>1.8) vs. those without elevated TBR. 2 group comparisons will be performed using Student's T-test if the outcome variable is normally distributed. Distributions will be tested for normality using the Wilk-Shapiro test and examination of the histogram distributions. If the outcome variable is not normally distributed, we will consider appropriate transformation to approximate a normal distribution. Alternatively, if distributions are non-normal despite the applied transformation, we will use nonparametric Wilcoxon rank sum test to compare the 2 groups. All tests will be 2-sided, and a p < 0.05 will be considered statistically significant.

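### In the Aim 1A models, a change in the effect estimate is named both as the sign of a confounder to control and as a sign of collinearity to remove, with nothing to decide between them

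*Combined protocol and SAP*

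**What the plan says.** All of the wording is in the Statistical Analysis Plan for Aim 1A, under Multivariate modeling. The outcomes are TBR and number of plaque lesions, and the neurocognitive and mood models are to use similar methods. Covariates are selected by a change-in-estimate approach, with no percentage given.

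- On confounders: "Confounders will be identified by observing changes in effect estimate" (the estimate is β).
- On collinearity, in the next clause: "colinearity will be identified by observing changes in effect estimate" (again β). A second criterion is then added: "as well as by using Variance Inflation Factor criterion". No VIF cut-off is given.
- On the consequence of a collinearity finding: "Colinearity among covariates will be identified and redundant covariates will be excluded from the model".
- On fixed adjustment: "We will control for age, gender, race, smoking, lipids, diabetes mellitus, WRAT 4 reading versus educational years, and hypertension". The data-driven step supplies the rest of the adjustment set, which the plan describes as "in addition to other potential confounders identified by methods above".

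TBR and plaque come from Baseline Study Part 2, which, according to the Subject Selection overview, "will be performed in a subset of 60 HIV-infected patients and 10 HIVnegative controls".

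**The concern.** The two clauses attach the same observation to opposite actions. A covariate that moves β is a confounder and should be controlled. A covariate that moves β may also be flagged as collinear and, if judged redundant, removed. The plan gives no size of change, standard-error criterion, VIF cut-off or order of precedence that would tell the analyst which applies.

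A confounder is related to the marker and does move its coefficient, so the β signal cannot tell a confounder from a redundant covariate. If a genuine confounder is removed on that signal, the marker's coefficient returns to its confounded value. Aim 1A uses these models to say which factors are independently associated with TBR and plaque, so such a removal could produce a false claim of independent association.

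**Working it through.** No sample size or power figure in the plan depends on this rule, so there is no stated figure to reproduce for it. The neighbouring Aim 1A figures do reproduce. The detectable correlations are 0.582, 0.328 and 0.290 for n = 20, 70 and 90 (stated 0.58, 0.33, 0.29), and d = 0.68 with 35 per group has 80.1% power (stated 80%).

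**Step 1. Does a change in β separate a confounder from a redundant covariate?**

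The check simulated Y = 0.3X + bC + e with n = 60 and 20,000 runs, where X is the marker and C the candidate covariate. The effect sizes, correlations and 10% change threshold are assumptions. With one covariate, VIF = 1/(1 − r²).

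| Candidate C | r with X | β for X changes by more than 10% | Median VIF |
|---|---|---|---|
| True confounder, b = 0.4 | 0.3 | 92% of runs | 1.10 |
| True confounder, b = 0.4 | 0.5 | 97% | 1.34 |
| True confounder, b = 0.4 | 0.7 | 96% | 1.98 |
| Redundant, b = 0 | 0.95 | 94% | 10.4 |

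The change in β looks the same in both situations. VIF separates them: for the true confounders the share of runs with VIF above 5 was 0.0%, and for the redundant covariate it was 99.9%. Results at n = 70 are similar. Dropping the confounder at r = 0.5 shifts the expected β from 0.30 to 0.30 + 0.4 × 0.5 = 0.50.

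**Step 2. What would dropping a confounder cost?**

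Take n = 60 (the imaged participants with HIV), two-sided 5%, a marker with no effect of its own, and one confounder with assumed correlation a with both marker and TBR. The crude marker–TBR correlation is then a². By Fisher z, the probability of significance is Φ(√57 · atanh(a²) − 1.96), plus a negligible opposite tail.

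- a = 0.4: a² = 0.16, VIF = 1/(1 − 0.16) = 1.19, √57 × 0.1614 = 1.218, probability 23%.
- a = 0.5: a² = 0.25, VIF = 1.33, √57 × 0.2554 = 1.928, probability 49%.
- a = 0.6: a² = 0.36, VIF = 1.56, √57 × 0.3769 = 2.845, probability 81% (82% with the t critical value and small-sample correction, which leave the other two at 23% and 49%).

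With the confounder kept in, the rate is the nominal 5%.

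**Step 3. How far do the eight named covariates protect?**

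Suppose they explain a share R² of the confounder's variance and relate to marker and TBR only through it. The marker–TBR correlation left after adjusting for them is a²(1 − R²)/(1 − a²R²), and √57 becomes √(60 − 3 − 8) = 7.

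| R² (assumed) | a = 0.4 | a = 0.5 | a = 0.6 |
|---|---|---|---|
| 0 | 20% | 43% | 75% |
| 0.50 | 9% | 17% | 35% |
| 0.75 | 6% | 8% | 14% |

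For example, with R² = 0.5 and a = 0.6: 0.18/0.82 = 0.220, 7 × 0.2231 = 1.56, and the probability is 35%.

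**The case against.** The strongest reply is that the paragraph read as a whole permits much less than the clause read alone.

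- **VIF is also named, and only redundant covariates go.** A reader might infer that every confounder meets the exclusion rule by definition. The text does not support that. If both criteria must be met, a confounder with a VIF of 1.2 to 1.6 stays in. What stands is that the wording does not say whether both criteria are needed or either is enough, and it gives no VIF cut-off.
- **Eight covariates are to be controlled in any case.** A reader might infer that the analyst may keep or drop any influential covariate. The unconditional commitment to the named list rules that out on its natural reading, although the list is not expressly exempted from the redundancy step. The exposure is mainly to the other potential confounders that the data-driven rule selects.
- **The two β's may differ.** For confounding, β is naturally the marker's coefficient. For collinearity among covariates it could be the covariates' own unstable coefficients. The clause may also be a drafting or text-extraction slip. Both are possible, but the text makes no such distinction and shows no gap.
- **The models are secondary to the trial's primary question.** This is correct. The primary TBR comparison between teduglutide and placebo is an independent samples t-test and does not use this rule. The point remains for Aim 1A, which reports independent associations at p < 0.05.

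**Conclusion.** The point holds as a defect in a stated rule: one signal is tied to two opposite actions, and nothing decides between them. It could license removal of a genuine confounder outside the named list at a VIF of only about 1.1 to 2. It reaches the Aim 1A models and the neurocognitive and mood models that follow similar methods.

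The figures of 23%, 49% and 82% are conditional, upper-end values. They assume a single confounder that is certainly dropped, carries all of the association, is equally correlated with marker and TBR, and is accompanied by no other adjustment. None of those correlations is in the documents. If the named covariates capture three quarters of that confounder, the rates fall to 6%, 8% and 14%. The figures show that the ambiguity can matter. They do not predict the error rate of this study. The correction is worth making because it is cheap and specific.

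**What to change.** In the multivariate modeling paragraph:

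1. Delete change in β as a criterion for collinearity.
2. Keep change-in-estimate for confounding only, applied to the marker's coefficient, with a stated percentage.
3. Define collinearity by VIF, standard-error inflation or both, with a cut-off stated in advance.
4. State that the named covariates, and any covariate kept as a confounder, are not removed because β moved.
5. Say how candidates on the hypothesised pathway, such as sCD163 and MCP-1, are handled. Aim 1A is cross-sectional, so their timing relative to the marker is unknown. They should be treated as possible mediators and not automatically kept as confounders.

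The cost is a few sentences in the plan and no new data. The statistical price is a somewhat larger standard error when a strongly related confounder stays in the model.
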